## 2 Introduction

This original Statistical Analysis Plan (SAP) V1.0 was written for Study AU-011-101 conducted in subjects with small to medium primary choroidal melanoma on the basis of Clinical Protocol Rev-7, 25 May 2018. The International Conference on Harmonization (ICH) guideline E3 "Structure and Content of Clinical Study Reports" was used as a guide to the writing of the plan.

The revision of the SAP was made on the basis of Clinical Protocol Protocol Rev-15, 21 Feb. 2020.

An overview of the changes made in the SAP v2.0:

- Revision of primary objective and secondary objectives.
- Addition of Expansion cohort (Cohort 9), Observational cohort (Cohort 10), and 2 Cycles of AU-011 cohorts (Cohort 11 and Cohort 12)
- The 2nd Interim Analysis was decided to be cancelled.
- Number of subjects in the study increased from 45 to 60.
- Number of study sites in the study increased from 10 to 15.
- Addition of the definitions of subgroups, and subgroup analyses.
- Revision of the definitions of Tumor control, Partial response and disease progression.
- Addition of tumor growth rate analysis.
- The final analysis would be performed after all subjects complete the Week 52 Visit.

An overview of the changes made in the SAP v3.0:

- Revision of tumor response assessment to consider various factors that could have impacted the determination of tumor response.
- Addition of a new analysis population: Efficacy Evaluable population, to exclude subjects from site 009 due to significant GCP deviations.
- Addition of analyses of ocular TEAEs related study drug/injection procedure/laser.

An overview of the changes made in the SAP v4.0:

- Redefined the ITT population (instead of the Efficacy Evaluable population) as the primary population for efficacy analysis.
- Revision of the criteria for subjects with an AE of pigmentary changes in the determination of tumor response.
- Addition of analyses of tumor response and visual acuity for site 009 subjects only.
- Addition of analyses of subjects with visual acuity preservation.

An overview of the changes made in the SAP v5.0 (after the 1st DB lock on 25 Aug. 2021):

- More details/clarification of rules given specifically for tumor response analysis at Month 12 LOCF and Last Visit.
- Revision of the criteria for visual acuity failure for consistency with the overall definition when data are not available at both Week 39 and Week 52.

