### **3.3 Sample Size Justification**

No formal sample size calculation was performed for this ascending single and repeat dose and cycle phase 1b/2 study. Approximately 60 subjects with small primary CM will be enrolled and treated with Light-activated AU-011 at 3 dose levels and repeat dose regimens and cycles of Light-activated AU-011 and one or two laser applications.

The study was designed to investigate at least 3 subjects at each treatment level and expand to investigate an additional 6 subjects at the maximum feasible dose. Provisions for expanding cohorts based on observed DLTs were also provided as per the study design section above.

Confidential

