## 4 General Analysis Definitions

Data will be analyzed using SAS (Version 9.4 or later).

No tests of significance will be carried out to compare cohorts on baseline data because any observed differences between them must be attributed to chance.

Since this is an exploratory study, no formal hypothesis testing will be performed. Descriptive statistics will be used to tabulate and summarize baseline, efficacy and safety outcomes.

Descriptive statistics will be tabulated as follows:

- Categorical data will be summarized in contingency tables presenting frequencies and percentages.
- Continuous data will be summarized using number of non-missing values (n), mean, standard deviation, median, minimum and maximum values.

The tables will be created by cohort and overall, in the order as listed in Section 4.5.4. In addition, a subtotal of dose escalation cohorts (Cohort 1 to 8) and a subtotal of the expansion cohorts (Cohort 9 to 12) will be included in all the relevant tables.

Listings with individual values will be provided for all data presented in the tables.

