### 4.3.2 Efficacy Evaluable Population

The Efficacy Evaluable population will consist of ITT population subjects, excluding subjects from site 009, who have been excluded based on site audit findings.

This population will be used as a sensitivity analysis for efficacy.

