### 4.3.3 Safety Population

The Safety population will include all subjects who received at least one administration of study treatment. Subjects will be analyzed according to the treatment that they actually received.

This is the primary population for the safety analysis.

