### 8.3 Sensitivity Analyses

The following sensitivity analyses will be performed:

- The maximum tumor thickness and largest basal diameter endpoints (i.e., as described in Sections 8.1.5 and 8.1.6, respectively) will be summarized on ITT population excluding post-standard of care data (i.e. all data after receiving standard of care will be excluded for the standard of care subjects).
- BCVA data (Section 8.2) will be summarized on ITT population excluding post-standard of care data. Number and percentage of subjects with a 5, 10 or 15 letter gain or loss at each visit up to the Week 52 visit and at the end of study visit will also be provided for: 1) Efficacy Evaluable population; 2) Efficacy Evaluable population excluding post-standard of care data.
- Tumor response (section 8.1.7) will be summarized on Efficacy Evaluable population.

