14.2.2.3	Number and Percentage of Subjects with Visual Acuity Preservation – Study Eye - ITT Population
14.2.2.4	Summary of Visual Acuity Score (ETDRS Letters) and Change from Baseline by Visit – Study Eye - ITT Population (Site 009 only)
14.2.2.5	Number and Percentage of Subjects with Visual Acuity Preservation – Study Eye - ITT Population (Site 009 only)
14.2.3.1.1	Sensitivity Analysis - Summary of Maximum Tumor Height (B-scan) and Change from Baseline in by Visit - Study Eye – ITT Population excluding all Post-standard of care data
14.2.3.1.2	Sensitivity Analysis - Summary of Largest Basal Diameter (Fundus Photography) and Change from Baseline by Visit - Study Eye – ITT Population excluding all Post-standard of care data

Confidential

14.2.3.2.1	Sensitivity Analysis - Summary of Visual Acuity Score (ETDRS Letters) and Change from Baseline by Visit – Study Eye - ITT Population excluding all Post-standard of care data
14.2.3.2.2	Sensitivity Analysis - Proportion of Subjects with 5, 10, 15 Letters Gain/Loss of Vision by Visit – Study Eye - ITT Population excluding all Post-standard of care data
14.2.3.2.3	Sensitivity Analysis - Proportion of Subjects with 5, 10, 15 Letters Gain/Loss of Vision by Visit – Study Eye – Efficacy Evaluable Population
14.2.3.2.4	Sensitivity Analysis - Proportion of Subjects with 5, 10, 15 Letters Gain/Loss of Vision by Visit – Study Eye – Efficacy Evaluable Population excluding all Post-standard of care data
14.2.3.3.1	Sensitivity Analysis - Summary Of Tumor Response (Method 1) – Study Eye - EFFICACY EVALUABLE Population
14.2.3.3.2	Sensitivity Analysis - Summary Of Tumor Response (Method 2) – Study Eye - EFFICACY EVALUABLE Population
14.2.3.3.3	Sensitivity Analysis - Summary Of Tumor Response (Method 3) – Study Eye - EFFICACY EVALUABLE Population
14.2.3.3.4	Sensitivity Analysis - Summary Of Overall Tumor Response (Method 1) – Study Eye - EFFICACY EVALUABLE Population
14.2.3.3.5	Sensitivity Analysis - Summary Of Overall Tumor Response (Method 2) – Study Eye - EFFICACY EVALUABLE Population
14.2.3.3.6	Sensitivity Analysis - Summary Of Overall Tumor Response (Method 3) – Study Eye - ITT Population
14.2.4.1	Summary of Subretinal Fluid by EDI-OCT (Shift Table) – Study Eye – ITT Population
14.2.4.2	Summary Of Central Retinal Thickness By EDI-OCT – Study Eye – ITT Population
14.2.5.1	Summary of Orange Pigmentation on Tumor as Measured by Fundus Photography (Shift Table) – Study Eye – ITT Population

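### Table 14.2.3.3.6, the sensitivity table for overall response by the primary Method 3, is listed on ITT and so does not exclude site 009; thickness, LBD and safety have no site-excluded summary

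*SAP*

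**What the plan says.** The SAP 2 summary of changes for v3.0 gives the reason for the EE population: "Efficacy Evaluable population, to exclude subjects from site 009 due to significant GCP deviations". The current definition in SAP 4.3.2 confirms that the site is excluded on audit findings and fixes the use: "This population will be used as a sensitivity analysis for efficacy". ITT, with site 009 included, is the primary efficacy population (SAP 4.3.1).

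SAP 8.1 names Method 3 as the primary way of describing response in the study report. For each method it plans by-visit results plus an overall table holding Month 12 LOCF and last visit. On sensitivity, SAP 8.3 says: "Tumor response (section 8.1.7) will be summarized on Efficacy Evaluable population". The table list in SAP 11.3.1 gives the overall Method 3 sensitivity table as "Sensitivity Analysis - Summary Of Overall Tumor Response (Method 3) – Study Eye - ITT Population".

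For safety, which is the primary objective (SAP 3.1.1), SAP 4.3.3 defines the Safety population as all treated subjects and adds: "This is the primary population for the safety analysis". SAP 9 uses that population throughout.

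**The concern.** A sensitivity table is meant to show whether the main result depends on the questioned site. If the table for the primary method is run on the main population, it agrees with the main table by construction and tests nothing.

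Method 3 is also a method in which site conduct can matter directly. Under SAP 8.1.2 and 8.1.3, an investigator's answer on the eCRF can turn a measured progression into stable disease, even though the images themselves are read centrally.

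Safety data depend on the site as well. Investigators grade adverse events and decide relatedness (Protocol 10.2.3.4). In Cohorts 1 to 9, after 30 days only events the investigator judges related are reported (Protocol 10.2.3.3). A DLT is a judgement about severity and cause (Protocol 8.4.1). If the deviations touched any of this, no planned safety summary would show it.

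**Working it through.** There is no plan figure to reproduce: "Since this is an exploratory study, no formal hypothesis testing will be performed", and "No formal sample size calculation was performed for this ascending single and repeat dose and cycle phase 1b/2 study". The check compares every entry of SAP 11.3.1 with SAP 4.3, 8.1, 8.3 and 9.

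**1. The response tables.**

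| Content | Main table (ITT) | Sensitivity table | Population listed for sensitivity |
|---|---|---|---|
| By visit, Method 1 | 14.2.1.3.1 | 14.2.3.3.1 | EE |
| By visit, Method 2 | 14.2.1.3.2 | 14.2.3.3.2 | EE |
| By visit, Method 3 | 14.2.1.3.3 | 14.2.3.3.3 | EE |
| Overall, Method 1 | 14.2.1.3.4 | 14.2.3.3.4 | EE |
| Overall, Method 2 | 14.2.1.3.5 | 14.2.3.3.5 | EE |
| Overall, Method 3 | 14.2.1.3.6 | 14.2.3.3.6 | ITT |

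Five of the six use EE. The sixth has the same summary, method, eye and population as its main table, so the two would differ by zero in every cell.

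**2. Whether the text overrides the list.** SAP 8.3 assigns EE by pointing to Section 8.1.7. That section describes results at each visit, across cohorts and for subgroups. It names neither Month 12 LOCF nor last visit; those come from the opening text of 8.1. So only the table list specifies an overall response table for this check, and there the Method 3 entry has the wrong population.

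**3. Coverage of site 009 across the list.**

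- On EE: 14.2.3.2.3 and 14.2.3.2.4 (letter gain or loss) and 14.2.3.3.1 to 14.2.3.3.5 (response), 2 + 5 = 7 tables.
- Site 009 only: 14.2.1.3.7 to 14.2.1.3.9 (overall response), 14.2.2.4 (mean BCVA) and 14.2.2.5 (acuity preservation), 3 + 2 = 5 tables, all efficacy.
- Thickness (14.2.1.1) and LBD (14.2.1.2): none of either kind. Their sensitivity versions, 14.2.3.1.1 and 14.2.3.1.2, drop data after standard of care but keep the site.
- Safety: 32 entries under 14.3. Thirty name the Safety population, two (14.3.4.3 and 14.3.4.4) name none and fall under SAP 9, and none excludes or isolates the site.

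**4. What can be recovered.** EE is ITT minus site 009, so for a count x and a size n:

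x(EE) = x(ITT) − x(009), and n(EE) = n(ITT) − n(009).

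For a mean m:

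m(EE) = [n(ITT)·m(ITT) − n(009)·m(009)] / [n(ITT) − n(009)].

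If the columns match, overall Method 3 without the site follows from 14.2.1.3.6 and 14.2.1.3.9. Acuity preservation follows from 14.2.2.3 and 14.2.2.5, and mean BCVA from 14.2.2.1 and 14.2.2.4. For thickness, LBD and safety the site-009 term is never tabulated, so only the subject listings remain.

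**The case against.** The strongest reply is that the ITT label is a slip. The table carries the sensitivity prefix, follows five EE siblings, and would make no sense as a planned rerun on ITT. A careful reader would notice the ITT label and denominators. This is very probably right. It lowers the weight of the point, but it does not make the entry correct, and SAP 8.3 does not settle it for the overall table.

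A reader might infer that EE is the only means of testing the site's influence. The documents do not support that. The five site-009-only tables are a second, pre-specified means, and by-visit Method 3 on EE is listed. Efficacy by the primary method is therefore not left unchecked.

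On thickness and LBD, central reading with averaging over two to three readers (SAP 8) limits the site's influence without removing it. Individual values are listed, so a determined reader could rebuild the summaries by hand. That stands, but it does not replace a table.

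On safety, the SAP restricts EE to efficacy and keeps every treated subject. That is a sound main analysis. The gap is an omission, not a contradiction. A reader might also infer that adverse event or DLT rates are biased by the site. The documents do not support that either: they do not say what the audit found, or that event capture or treatment delivery was affected.

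**Conclusion.** The point holds in a limited form. One table is wrong as listed, and it is the sensitivity version of the overall result by the primary method. As written, it differs from its main table by zero. The result it should show is largely recoverable by subtraction, provided the site-009-only table uses the same columns.

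The more substantive gap is that change in thickness, change in LBD and all 32 safety entries have no summary that excludes or isolates site 009, although safety is the primary objective.

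No numerical effect can be given. The number of subjects at the site is not stated, though it will become visible at reporting because SAP 5.1 tabulates the size of each population. The kind of deviation is not stated either. Any figure for bias in event rates would rest wholly on assumed site size, event rate and degree of under-reporting.

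**What to change.** 1. In SAP 11.3.1, change the population of Table 14.2.3.3.6 to Efficacy Evaluable.
2. In SAP 8.3, name the Month 12 LOCF and last-visit response summaries alongside the by-visit results of Section 8.1.7.
3. Add EE versions of Tables 14.2.1.1 (thickness) and 14.2.1.2 (LBD).
4. In SAP 9, keep the full Safety population as primary and add supplementary versions excluding site 009 of Tables 14.3.1.1 (exposure), 14.3.1.3 (DLTs), 14.3.2.1 (TEAE overview, which already includes SAE and fatal AE counts) and 14.3.2.3.1-7 (ocular TEAEs, study eye).

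The cost is one corrected title, one added sentence in SAP 8.3, and re-runs of existing programs with a site filter. The downside is more output on smaller numbers. In a 3-subject cohort one subject is already 1/3, or 33 percentage points; if one of the three is removed, each remaining subject is 1/2, or 50 points. The site-excluded safety tables are therefore best read on the subtotals and the overall column.

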### 11.3.2 List of Graphs

Graph Number	Title
14.2.1.1	Mean Change in Maximum Tumor Thickness from Baseline as Measured by B-scan Ultrasound – ITT Population
14.2.1.2	Mean Change in Largest Tumor Basal Diameter as Measured by Fundus Photography – ITT Population
14.2.1.3	Mean Change in Visual Acuity (in ETDRS Letters) Over Time – ITT Population
14.2.2.1	Sensitivity Analysis - Mean Change in Maximum Tumor Thickness from Baseline as Measured by B-scan Ultrasound – ITT Population excluding all Post-standard of care data
14.2.2.2	Sensitivity Analysis - Mean Change in Largest Tumor Basal Diameter as Measured by Fundus Photography – ITT Population excluding all Post-standard of care data
14.2.2.3	Sensitivity Analysis - Mean Change in Visual Acuity (in ETDRS Letters) Over Time – ITT Population excluding all Post-standard of care data

### 11.3.3 List of Derived Data Listings

Listing Number	Title
16.1.1	Listing of Early Discontinuations of Study – ITT Population
16.1.2.1	Listing of Protocol Deviation Details – ITT Population
16.1.2.2	Listing of Inclusion and Exclusion Criteria Not Met – ITT Population
16.1.3	Listing of Demographics and other Baseline Characteristics – ITT Population
16.1.4.1	Listing of Ophthalmic History – ITT Population
16.1.4.2	Listing of Other Medical History – ITT Population
16.1.5	Listing of Baseline Ophthalmic Examinations Information – ITT Population
16.1.6.1	Listing of Prior and Concomitant Medications – ITT Population
16.1.6.2	Listing of Prior and Concomitant Procedures/Surgeries – ITT Population
16.2.1	Listing of B-scan Parameters – Study Eye – ITT Population
16.2.2	Listing of Fundus Photos Parameters – Study Eye – ITT Population
16.2.3	Listing of BCVA Parameters – Study Eye – ITT Population
16.2.4	Listing of EDI-OCT Parameters – Study Eye – ITT Population
16.2.5	Listing of FA Parameters – Study Eye – ITT Population
16.2.6	Listing of A-scan Parameters – Study Eye – ITT Population
16.2.7	Listing of OCTA Parameters – Study Eye – ITT Population
16.3.1	Listing of Exposure to AU-011 and Laser – SAF Population
16.3.2	Listing of Dose Limiting Toxicities – SAF Population
16.3.3.1	Listing of Adverse Events – SAF Population
16.3.3.2	Listing of Serious Adverse Events – SAF Population
16.3.3.3	Listing of Fatal Adverse Events – SAF Population
16.3.4	Listing of Laboratory Data – SAF Population
16.3.5	Listing of Vital Signs – SAF Population
16.3.6	Listing of Slit Lamp Biomicroscopy Results – Study Eye – SAF Population
16.3.7	Listing of Tonometry Results – Study Eye – SAF Population
16.3.8	Listing of Fundoscopy Results – Study Eye – SAF Population
16.3.9	Listing of Visual Field Exam – Study Eye – SAF Population
16.3.10	Listing of Anti-Drug Antibodies – SAF Population
16.3.11	Listing of Additional Therapies – SAF Population
